- ^l Collection will be predose on days of dosing and for days without dosing, at any time that visit day, and combined with urine stabilizing buffer. All collection times will be recorded in the eCRF.
- ^m A predose serum sample will be collected on Days 1079, 1247, 1415, 1639, and 1807. A serum sample will also be collected at any time on Day 1863 or ET. For patients who discontinue treatment but remain in the study, ADA sample will be collected at any time during the visits until approximately 39 weeks after the last dose of ALXN1210. In case of retreatment, if the patient starts the retreatment on a scheduled visit which does not include ADA sample collection, a predose ADA sample must be collected. If a supplemental dose is administered, a predose ADA sample will be collected. All collection times will be recorded in the eCRF.
- ⁿ Review the Clinical Trial Participant Safety Information Card with the patient and discuss the importance of carrying the safety card at all times, and the risks ALXN1210 treatment, including the risk of meningococcal infection.
- ^o Concomitant medications must be collected at all study visits (and at the 56 [± 5]-day follow-up phone call for patients who terminate the study early) and checked against the prohibited medication listed in [Section 9.7](#).
- ^p The dose of ALXN1210 is based on the patient's body weight recorded at the last visit or more recently. For patients who discontinue ALXN1210 treatment, remain in the study, and further receive retreatment, the dosing details are provided in [Section 8.3.2.1](#).

8. STUDY POPULATION

A total of approximately 55 patients with documented aHUS will be enrolled and assigned to treatment with ALXN1210 at approximately 200 investigative sites globally. The study will enroll at least 6 and up to 10 adolescent (12 to < 18 years of age at Screening) patients and at least 10 and up to 25 patients with prior kidney transplants. A minimum of 30 patients who meet all laboratory criteria for TMA (platelet count of < 150,000 per microliter, LDH $\geq 1.5 \times$ upper limit of normal (ULN), hemoglobin \leq lower limit of normal (LLN), and serum creatinine level \geq ULN) as determined by the central laboratory at Day 1, will be enrolled.

Individuals who do not satisfy the criteria for participation in this study (screen failure) may be rescreened based on discussion and agreement between the Investigator and the Medical Monitor. Patients may be rescreened a maximum of 2 times.

Prospective approval of protocol deviations to recruitment and enrollment criteria, also known as protocol waivers or exemptions, is not permitted.

8.1. Inclusion Criteria

Patients are eligible for enrollment in the study only if they meet all of the following criteria and none of the exclusion criteria:

1. Male or female patients ≥ 12 years of age and weighing ≥ 40 kg at the time of consent.
2. Evidence of TMA, including thrombocytopenia, evidence of hemolysis, and kidney injury, based on the following laboratory findings:
 - a. Platelet count < 150,000 per microliter (μL) during the Screening Period or within 28 days prior to the start of the Screening Period, **and**
 - b. LDH $\geq 1.5 \times$ upper limit of normal (ULN) during the Screening Period or within 28 days prior to the start of the Screening Period, and hemoglobin \leq lower limit of normal (LLN) for age and gender during the Screening Period or within 28 days prior to the start of the Screening Period, **and**
 - c. Serum creatinine level \geq ULN during the Screening Period in adults (≥ 18 years of age), or $\geq 97.5^{\text{th}}$ percentile for age ([Appendix A](#)) at Screening in adolescents (12 to < 18 years of age) (patients who require dialysis for acute kidney injury are also eligible).
3. Among patients with a kidney transplant:
 - a. Known history of aHUS prior to current kidney transplant, **or**
 - b. No known history of aHUS, and persistent evidence of TMA at least 4 days after modifying the immunosuppressive regimen (eg, suspending or reducing the dose) of calcineurin inhibitor ([CNI]; eg, cyclosporine, tacrolimus) or mammalian target of rapamycin inhibitor ([mTORi]; eg, sirolimus, everolimus).
4. Among patients with onset of TMA postpartum, persistent evidence of TMA for > 3 days after the day of childbirth.
5. To reduce the risk of meningococcal infection (*Neisseria meningitidis*), all patients must be vaccinated against meningococcal infections within 3 years prior to, or at the time of,

initiating study drug. Patients who receive a meningococcal vaccine less than 2 weeks before initiating ALXN1210 treatment must receive treatment with appropriate prophylactic antibiotics until 2 weeks after vaccination. Patients who have not been vaccinated prior to initiating ALXN1210 treatment should receive prophylactic antibiotics prior to and for at least 2 weeks after meningococcal vaccination.

6. Patients < 18 years of age must have been vaccinated against *Haemophilus influenzae* type b (Hib) and *Streptococcus pneumoniae* according to national and local vaccination schedule guidelines.
7. Female patients of childbearing potential and male patients with female partners of childbearing potential must follow protocol-specified guidance ([Section 9.10](#)) for avoiding pregnancy while on treatment and for 8 months after last dose of study drug.
8. Willing and able to give written informed consent and comply with the study visit schedule. For patients < 18 years of age, patient's legal guardian must be willing and able to give written informed consent and the patient must be willing to give written informed assent (if applicable as determined by the central or local Institutional Review Board [IRB]/ Institutional (or Independent) Ethics Committee [IEC]).

Evaluation of Inclusion Criteria 2a and 2b may be based on local laboratory results within 28 days prior to the start of the Screening Period or laboratory results obtained during the Screening Period from a local or central laboratory. If a local laboratory is used to define eligibility, additional samples will be collected during the Screening Period for LDH, platelet count, hemoglobin and serum creatinine and tested at the central laboratory. If patients are found to not meet the eligibility criteria for serum creatinine (Inclusion Criterion 2c) based on central laboratory results, they must not be enrolled into the study; if the subject has received the first dose of ALXN1210 the patient must be withdrawn from the study, and may be replaced. All analyses in this study will be based on results from the central laboratory. A central laboratory result for Inclusion Criterion 2c may not be available prior to first dose; results received after the first dose indicating that eligibility is not satisfied could lead to discontinuation and replacement of the patient.

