PK/PD sampling ^l		X ^l		X ^l		X ^l	X ^l	X ^l	X ^l	X ^l	X ^l	X ^l	X ^l	X ^l	X ^l	X ^l	X ^l	X ^l
Exploratory APC activity ^m		X		X			X		X		X		X		X			X
Exploratory serum and plasma biomarkers ⁿ		X		X					X				X					X
Exploratory urine biomarkers ^o		X		X					X				X					X
Exploratory urine ALXN1210 ^p		X		X		X			X									
Exploratory autoantibody ^q		X							X									
Exploratory genetic sample ^r		X																
Immunogenicity (ADA) ^s		X							X				X					X
Review safety card ^t		X	X	X	X	X	X	X	X	X	X	X	X	X	X	X	X	X
Concomitant medications ^u																		
Adverse events																		
ALXN1210 administration ^v		X		X					X				X					

Table 1: Schedule of Study Visits and Assessments: Screening Through End of Initial Evaluation Period (Continued)

Abbreviations: ADA = antidrug antibody; ADAMTS13 = a disintegrin and metalloproteinase with a thrombospondin type 1 motif, member 13; aHUS = atypical hemolytic uremic syndrome; APC = alternative pathway of complement; ECG = electrocardiogram; EOI = end of infusion; EQ-5D-3L = EuroQol 5 dimensions 3 level; ET = early termination; FACIT = functional assessment of chronic illness therapy; HUS = hemolytic uremic syndrome; LDH = lactate dehydrogenase; N/A = not applicable; PD = pharmacodynamics; PK = pharmacokinetics; QoL = quality of life; ST-HUS = Shiga toxin-related hemolytic uremic syndrome

- ^a All patients must be vaccinated against meningococcal infections within 3 years prior to, or at the time of, initiating study drug. Patients who initiate study drug treatment less than 2 weeks after receiving a meningococcal vaccine must receive treatment with appropriate prophylactic antibiotics until 2 weeks after vaccination. Patients who have not been vaccinated prior to initiating ALXN1210 treatment should receive prophylactic antibiotics prior to and for at least 2 weeks after meningococcal vaccination.
- ^b Stool sample.
- ^c Female patients of childbearing potential only. Serum pregnancy test at Screening and Day 183/ET; urine or serum pregnancy test at all other required time points. A negative pregnancy test result is required prior to administering study drug to female patients of childbearing potential at the indicated study visits.
- ^d FACIT Fatigue version 4 will be used for patients ≥ 18 years of age at Screening. Pediatric FACIT Fatigue will be used for patients < 18 years of age at Screening.
- ^e On dosing days, patient-reported assessments will be performed prior to dosing.

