9.8. Vaccination

Due to its mechanism of action, the use of ALXN1210 increases the patient's susceptibility to infection. To reduce the risk of infection, all patients must be vaccinated against *N. meningitidis*.

Patients must be vaccinated against *N. meningitidis* within 3 years prior to, or at the time of, receiving the first dose of ALXN1210. Patients who will be treated with drug less than 2 weeks after receiving a meningococcal vaccine must receive treatment with appropriate prophylactic antibiotics until 2 weeks after vaccination. Vaccines against serotypes A, C, Y, W135, and B, where available, are recommended to prevent common pathogenic meningococcal serotypes. Patients must be vaccinated or revaccinated according to current national vaccination guidelines or local practice for vaccination use with complement inhibitors (eg, eculizumab).

It is recognized that some patients who have not been vaccinated against *N. meningitidis* within 3 years prior to receiving the first dose of ALXN1210 may not be able to receive a vaccination at the time of the first dose. Patients who have not been vaccinated prior to initiating ALXN1210 treatment should receive prophylactic antibiotics prior to and for at least 2 weeks after meningococcal vaccination.

Vaccination may not be sufficient to prevent meningococcal infection. Consideration should be given per official guidance and local practice on the appropriate use of antibacterial agents. All patients should be monitored for early signs of meningococcal infection, evaluated immediately if infection is suspected, and treated with appropriate antibiotics, if necessary.

To increase risk awareness and promote quick disclosure of any potential signs or symptoms of infection experienced by the patients during the course of the study, patients will be provided a safety card to carry with them at all times and for 8 months after last dose of ALXN1210.

Additional discussion and explanation of the potential risks, signs, and symptoms will occur at specific time points as part of the review of the patient safety card and throughout the study as described in the Schedule of Assessments (Table 1, Table 2, and Table 3).

Patients < 18 years of age must also be vaccinated against *Haemophilus influenzae* type b (Hib) and *Streptococcus pneumoniae* according to national and local vaccination schedule guidelines, prior to, or at the time of, receiving the first dose of ALXN1210.

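### Antibiotic cover is a 'must' for recently vaccinated patients but only a 'should', timed from vaccination, for patients who start ALXN1210 unvaccinated, and no scheduled vaccination check follows Screening

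*Protocol*

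**What the plan says.** Inclusion Criterion 5 (Protocol Section 8.1, repeated in the synopsis) has three parts. It opens with a universal requirement: "all patients must be vaccinated against meningococcal infections within 3 years prior to, or at the time of" starting study drug. It then makes cover mandatory for recent vaccinees: "Patients who receive a meningococcal vaccine less than 2 weeks before initiating ALXN1210 treatment must receive treatment with appropriate prophylactic antibiotics", continuing until 2 weeks after the vaccine. It ends with patients who start without a vaccine: "Patients who have not been vaccinated prior to initiating ALXN1210 treatment should receive prophylactic antibiotics", before vaccination and for at least 2 weeks after it.

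Table 1 footnote a (Section 7.3) follows the same pattern: "Patients who initiate study drug treatment less than 2 weeks after receiving a meningococcal vaccine must receive treatment with appropriate prophylactic antibiotics", while the unvaccinated "should receive prophylactic antibiotics prior to and for at least 2 weeks after meningococcal vaccination". Section 9.8 has the mandatory sentence as "Patients who will be treated with drug less than 2 weeks after receiving a meningococcal vaccine must receive treatment with appropriate prophylactic antibiotics". It also accepts that some patients without a vaccine in the preceding 3 years "may not be able to receive a vaccination at the time of the first dose", and repeats the *should* sentence for those who start unvaccinated.

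Section 5.1.2.1 names meningococcal infection as the drug's main risk and refers to Section 9.8 for the mitigation.

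**The concern.** A patient who begins C5 blockade without a vaccine has less protection than one vaccinated a few days earlier, yet the firmer verb is reserved for the second patient. Read literally, the rule lets an unvaccinated patient start treatment without mandatory cover from the first dose, and leaving the antibiotics out is not clearly a protocol deviation.

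The eligibility wording adds to the problem. A site with an urgent, unvaccinated patient finds one sentence of Criterion 5 that excludes the patient and another that says how to manage the patient. Section 8 rules out waivers, so the site cannot settle the matter by asking for one.

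What is at stake is patient safety on the one risk that the protocol singles out, and consistent conduct across about 200 sites.

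**Working it through.** No arithmetic applies beyond a count. The check sets the statements side by side and then reads the schedule.

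**1. The verb.**

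| Place in the Protocol | Vaccinated less than 2 weeks before treatment | Starts unvaccinated |
|---|---|---|
| Synopsis, Inclusion 5 | must | should |
| Section 8.1, Inclusion 5 | must | should |
| Section 7.3, Table 1 footnote a | must | should |
| Section 9.8 | must | should |

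The pattern holds in 4 of 4 places. No other section makes cover mandatory for the right-hand column. The further sentence in Section 9.8 on antibacterial agents asks only that their use be considered in line with guidance and local practice.

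**2. Whether the *must* can reach unvaccinated starters.** In the synopsis, Section 8.1 and footnote a, it is tied to starting treatment after a vaccine, which these patients have not had. Section 9.8 is looser. It speaks of being treated within 2 weeks of a vaccine, so it appears to cover same-day vaccination and might reach a vaccine given after Day 1. Under every wording, though, a vaccine must already have been given. Between the first dose and a later vaccination, only the *should* sentence applies.

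**3. The time anchor.** The *should* sentence runs from before vaccination to at least 2 weeks after it. It does not say that antibiotics start before the first dose. For a patient vaccinated later, the literal text is met by cover that begins shortly before the vaccine.

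**4. Eligibility.** Criterion 5 requires vaccination by the first dose for all, then provides for patients not vaccinated by then. Section 9.8 confirms that this group is expected. SAP Section 7.1.2 identifies by program any patient who violated an inclusion criterion. An unvaccinated starter could therefore be listed as an important deviation even though Section 9.8 foresees the case.

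**5. The schedule.** The vaccination row in Table 1 has one mark, at Screening. Tables 2 and 3 have no such row. Scheduled vaccination checks after Screening: 0.

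**6. What later visits do contain.**
- Concomitant medications are collected at every visit but compared with the prohibited list, not with required cover.
- Safety card review, from Day 1, addresses awareness of the risk.
- Vaccination status goes on the eCRF with no time point stated.

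These would record a late vaccine or antibiotic once given. None is described as prompting the site when one is missing.

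**7. Effect on efficacy.** Criterion 5 is not among the criteria that define the Full Analysis Set or the Per Protocol Set (SAP Sections 6.1 and 6.2), so the efficacy analyses do not change.

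**The case against.** The strongest reply is that *should* in this protocol does not mean optional. The verbs are not defined, and *should* governs acts that nobody would treat as discretionary: aseptic preparation (Section 9.1.4), not freezing the drug (9.1.3), permanent discontinuation after a serious infusion reaction (8.3.2) and recording adverse events from consent (11.7). On that view unvaccinated starters have a real instruction. It even asks for longer cover than the *must* sentence, because it includes time before the vaccine. This stands in part. A reader might infer that these patients have no antibiotic instruction at all, or that the protocol makes antibiotics optional; the documents do not support either. What remains is that two adjacent sentences use different verbs for the same measure, and a site may reasonably read the difference as intended.

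A second reply points to the safeguards. Section 9.8 says "Patients must be vaccinated or revaccinated according to current national vaccination guidelines or local practice for vaccination use with complement inhibitors" and asks for monitoring and prompt treatment of suspected infection. Medication use and procedures must be recorded (9.6), meningococcal infection is the targeted adverse event (11.7.1), and an independent committee reviews safety (16.2). All of this is correct and lowers the risk. None of it fixes when cover starts or schedules a check that the late vaccine was given. The eCRF is not among the documents, so it may contain a prompt that cannot be seen here.

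A third reply is that the group is narrow, since vaccination by the first dose is an inclusion requirement, and that a firm duty could keep a patient from urgent treatment. Section 5 cites acute mortality as high as 15% before eculizumab. The proposed duty needs antibiotics only to begin before the first dose, so urgent treatment stays possible for nearly everyone. The rare patient who can take neither vaccine nor antibiotic would be excluded, and that is a genuine cost.

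**Conclusion.** The point holds as a cheap improvement on patient safety. The wording is weakest for the least protected patients in 4 of 4 places, their cover is timed from vaccination and not from the first dose, Criterion 5 contradicts itself on whether they may be treated, and no scheduled vaccination check follows Screening.

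The size of the risk cannot be given. The documents state neither how many patients start unvaccinated nor any infection rate. A reader might want to count days without cover or patients exposed. Either figure would need assumed vaccination dates, an assumed share of patients and a particular reading in Section 9.8 of what being treated with the drug means, and the documents supply none of these. Nor does the text show that any patient would in practice go without antibiotics.

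The conclusion rests on reading the two verbs as different in force where they stand side by side. If the sponsor intends both as binding, the change only makes that plain; the time anchor, the eligibility conflict and the missing check would still need correction.

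**What to change.** 1. In the synopsis, Section 8.1 Inclusion 5, Table 1 footnote a and Section 9.8, replace the *should* sentence with wording to this effect: *A patient not vaccinated by the first dose must receive prophylactic antibiotics, started before that dose and continued until at least 2 weeks after meningococcal vaccination. The vaccine is to be given as soon as feasible under national guidelines or local practice.*
2. Add *except as stated below* to the sentence that requires all patients to be vaccinated.
3. For these patients only, record the vaccination date and whether cover continues, at existing visits from Day 15 until cover is complete. No fixed deadline for the vaccine is proposed; repeating the item until cover is complete keeps any delay visible.

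The cost is wording in four places and one conditional eCRF item at visits that already take place, with no extra visit, sample or patient. The downsides are slightly more data entry, a firmer duty on sites, and ineligibility of the rare patient who can take neither vaccine nor antibiotic before the first dose.

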8.2. Exclusion Criteria

Patients will be excluded from study enrollment if they meet any of the following criteria:

1. Known familial or acquired 'a disintegrin and metalloproteinase with a thrombospondin type 1 motif, member 13' (ADAMTS13) deficiency (activity < 5%). Eligibility may be defined using results from tests carried out as standard of care for the treatment of the current TMA prior to a patient giving informed consent. In these cases informed consent will be provided prior to collecting the data for the trial.
2. Known Shiga toxin-related hemolytic uremic syndrome (ST-HUS) as demonstrated by a positive test for Shiga toxin or culture of Shiga toxin producing bacteria. Eligibility may be defined using results from tests carried out as standard of care for the treatment of the current TMA prior to a patient giving informed consent. In these cases informed consent will be provided prior to collecting the data for the trial.

3. Positive direct Coombs test. Eligibility may be defined using results from tests carried out as standard of care for the treatment of the current TMA prior to a patient giving informed consent. In these cases informed consent will be provided prior to collecting the data for the trial.
4. Known Human Immunodeficiency Virus (HIV) infection.
5. Unresolved meningococcal disease.
6. Patients with a confirmed diagnosis of ongoing sepsis defined as positive blood cultures within 7 days prior to the start of Screening and untreated with antibiotics.
7. Presence or suspicion of active and untreated systemic bacterial infection that, in the opinion of the Investigator, confounds an accurate diagnosis of aHUS or impedes the ability to manage the aHUS disease.
8. Pregnancy or breastfeeding.
9. Heart, lung, small bowel, pancreas, or liver transplant.
10. Among patients with a kidney transplant, acute kidney dysfunction within 4 weeks of transplant consistent with the diagnosis of acute antibody-mediated rejection (AMR) according to Banff 2013 criteria ([Appendix B](#)).
11. Among patients without a kidney transplant, history of kidney disease other than aHUS, such as:
 - a. Known kidney biopsy finding suggestive of underlying disease other than aHUS
 - b. Known kidney ultrasound finding consistent with an alternative diagnosis to aHUS (eg small kidneys for age)
 - c. Known family history and/or genetic diagnosis of noncomplement mediated genetic renal disease (eg, focal segmental glomerulosclerosis)
12. Identified drug exposure-related HUS.
13. Receiving PE/PI, for 28 days or longer, prior to the start of Screening for the current TMA.
14. History of malignancy within 5 years of Screening with the exception of a nonmelanoma skin cancer or carcinoma in situ of the cervix that has been treated with no evidence of recurrence.
15. Bone marrow transplant (BMT)/hematopoietic stem cell transplant (HSCT) within the last 6 months prior to the start of Screening.
16. HUS related to known genetic defects of cobalamin C metabolism.
17. Known systemic sclerosis (scleroderma), systemic lupus erythematosus (SLE), or antiphospholipid antibody positivity or syndrome.
18. Chronic dialysis (defined as dialysis on a regular basis as renal replacement therapy for ESKD).
19. Patients receiving chronic intravenous immunoglobulin (IVIg) within 8 weeks prior the start of Screening, unless for unrelated medical condition (eg, hypogammaglobinemia); or chronic rituximab therapy within 12 weeks prior to the start of Screening.

20. Patients receiving other immunosuppressive therapies such as steroids, mTORi (eg, sirolimus, everolimus), CNI (eg, cyclosporine or tacrolimus) are excluded unless:
 - a. part of an established post-transplant antirejection regimen, or
 - b. patient has confirmed anti-complement factor antibodies requiring immunosuppressive therapy, or
 - c. steroids are being used for a condition other than aHUS (eg, asthma).
21. Participation in another interventional treatment study or use of any experimental therapy within 30 days before initiation of study drug on Day 1 in this study or within 5 half-lives of that investigational product, whichever is greater.
22. Prior use of eculizumab or other complement inhibitors.
23. Hypersensitivity to any ingredient contained in the study drug, including hypersensitivity to murine proteins.
24. Any medical or psychological condition that, in the opinion of the Investigator or Sponsor, could increase the risk to the patient by participating in the study or confound the outcome of the study.
25. Known or suspected history of drug or alcohol abuse or dependence within 1 year prior to the start of Screening.
26. Use of tranexamic acid within 7 days prior to Screening is prohibited.

Laboratory results for Exclusion Criterion number 1 and/or Exclusion Criterion number 2 may not be available prior to first dose. Later results for Exclusion Criterion number 1 and/or Exclusion Criterion number 2 could lead to discontinuation and replacement of the patient (please refer to [Section 8.3](#) for potential discontinuation and replacement details).

